## Hospital Study Drug Administration

We estimate that only a small proportion (<5%) of enrolled subjects will be hospitalized. If that does occur, subjects will continue on the study protocol as described for home study drug administration, as done in previous studies. Future unscheduled hospitalization at a non-study hospital site is even less common: none of the 274 patients enrolled in our pilot study were admitted to a different institution after evaluation. To minimize the impact that such an event could have on this trial, caregivers will be provided with a letter that they will be instructed to share with their pediatrician and with the admitting physician. The letter will describe the study, the care-plan, and it will include site investigator contact information and the importance of adhering to the study protocol.

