## 5.2 Secondary Study Outcomes

Secondary outcomes will include three of the individual components of the Modified Vesikari Score considered independently and one additional measure of burden of illness. Specifically, they are:

1. **Diarrhea duration:** Time from randomization until the appearance of the last watery stool as reported during daily surveys.
2. **Vomiting duration:** Time from randomization until the last vomiting episode as reported during daily surveys. Vomiting duration is only evaluated in children who vomited  $\geq 3$  times during the 24 hours prior to the emergency department visit.

3. **Return visits:** Return visits for unscheduled care to a healthcare provider related to vomiting, diarrhea, dehydration, fever, or fluid refusal, within 2 weeks of the index visit. Scheduled visits (e.g. reassessment, vaccinations, unrelated issues) will not be included.
4. **Missed daycare:** Days of daycare missed by subjects who attend daycare.
5. **Missed work:** Days of work missed by caregivers who work outside of the home.
6. **Household transmission rate:** A household census will be obtained at the time of enrollment, and information about household contacts symptoms will be obtained during daily surveys to determine household transmission rate.

The overall significance level for statistical tests on the secondary outcomes will be set at 0.05. Holm's method will be used to adjust for multiple comparisons. The continuous variables of duration of diarrhea and duration of vomiting (measured in hours and analyzed with a Van Elteren test), will be stratified by clinical center. Similarly, the number of days the child is absent from daycare and the caregiver is absent from work will be analyzed with a Van Elteren test, stratified by clinical center and etiology.

Dichotomous outcomes to be evaluated include emergency department acute gastroenteritis-related revisits, intravenous rehydration, and hospitalization. Additional analyses involving these outcomes will include linear and logistic regression models that adjust for possible effects of baseline characteristics.

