**Seriousness:** The severity of clinical adverse events and laboratory abnormalities will be recorded by the site investigator and categorized. A serious adverse event (SAE) is an adverse event that:

- results in death; or
- is life-threatening (the patient was, in the view of the site investigator, in immediate danger of death from the event as it occurred); or
- requires inpatient hospitalization or prolongs an existing hospitalization; or
- results in persistent or significant disability or incapacity; or
- results in congenital anomaly/birth defect; or
- any other event that, based upon appropriate medical judgment, may jeopardize the subject's health and may require medical or surgical intervention to prevent one of the other outcomes listed in this definition.

**Expectedness of the Event:** All adverse events, including serious adverse events, will be evaluated as to whether their occurrence was expected or unexpected. An adverse event is considered expected if it is known to be associated with acute gastroenteritis (acute gastroenteritis), other underlying medical conditions of the subject, is directly related to study outcome, or is otherwise mentioned in the protocol, informed consent, investigator brochure, or other study documents. Expected complications of acute gastroenteritis include abnormal taste, malaise, abdominal distention, foul smelling stools, dehydration, electrolyte and other laboratory abnormalities, other symptoms associated with viral syndromes, systemic infection and co-infection, seizures, and hospital admission.

**Treatment or Action Taken:** For each adverse event, the site investigator will record whether an intervention was required:

- Intervention: Surgery or procedure
- Other Treatment: Medication initiation, change, or discontinuation
- None: No action taken

**Outcome of Event:** Finally, the site investigator will record the clinical outcome of each adverse event as follows:

- Death
- Recovered and the patient returned to baseline status
- Recovered with permanent sequelae
- Symptoms continue

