# 2 Study Objectives and Outcomes

## 2.1 Study Objectives

### 2.1.1 Primary Objectives

The primary objectives of the Probiotics trial are:

1. to test the hypothesis that, in children with acute gastroenteritis, probiotic administration in the emergency department will decrease the likelihood of moderate-severe disease, defined by a validated Modified Vesikari Score (MVS)  $\geq 9$ , compared to placebo.
2. to test the hypothesis that, in children with acute gastroenteritis, probiotic administration will not be associated with serious adverse events, and will have a similar rate of side effects (e.g., bloating, fever, abdominal distention) as compared to placebo-treated children.

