### 7.4.2 Adverse Events

Adverse events (AEs) will be recorded from the time of randomization through 35 days. Symptoms/side-effects described previously will generally not be counted as AEs, as they will be reported separately. Serious adverse events (SAEs), unexpected medically attended events, and new chronic illnesses will be reported from randomization through one year after last study dose. Adverse events will be coded using the Medical Dictionary for Regulatory Activities (MedDRA), version 14.0.

**All Adverse Events** Summaries of incidence rates (frequencies and percentages), intensity, and relationship to study of individual AEs by System Organ Class and Preferred Term (MedDRA) will be prepared. All AEs beginning after randomization but before discharge will be included. Basic summaries by assigned groups will be prepared. The DSMB may request to see more detailed tables. The occurrence of any adverse event will be considered as a dichotomous outcome and will be compared between groups using a Mantel-Haenszel test, stratified by clinical center and duration of symptoms.

**Serious Adverse Events/Deaths** SAEs/Deaths will be reported separately in a similar fashion to the more general AE reports. In addition, narratives will be available for each event.

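### The only between-arm SAE comparison that SAP 7.4.2 implies is a pooled difference test without a margin or interval; it cannot support 'not associated with SAEs', and a fall in gastroenteritis admissions can offset a rise in other SAEs within it

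*Combined protocol and SAP*

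**What the plan says.** **The objective.** SAP v1.2 section 2.1.1 sets out to test that "probiotic administration will not be associated with serious adverse events, and will have a similar rate of side effects". No margin is attached to either half.

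**The SAE analysis.** Section 7.4.2 gives one sentence on method, "SAEs/Deaths will be reported separately in a similar fashion to the more general AE reports", and adds a narrative for each event. The AE report it points to has two parts. One is descriptive: incidence, intensity and relationship to study for "individual AEs by System Organ Class and Preferred Term (MedDRA) will be prepared". The other is a test: "The occurrence of any adverse event will be considered as a dichotomous outcome and will be compared between groups using a Mantel-Haenszel test".

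**What counts as an SAE.** Protocol V3.0 section 8.3.1 includes any adverse event that "requires inpatient hospitalization or prolongs an existing hospitalization". It lists dehydration and hospital admission as expected complications of gastroenteritis, so they are labelled as expected, not removed. Section 8.3.3 does not record a condition present at randomization that is unchanged or improving, but does record one that worsens. SAP 7.4.2 generally leaves the listed symptoms out of the AE count; that list (SAP 2.2.2) contains neither dehydration nor admission.

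**The same events as efficacy outcomes.** Hospital admission scores 2 points under Treatment in the Modified Vesikari Score (SAP 7.2, Table 1; a direct index admission only if longer than 48 hours). Hospitalization is also a tertiary outcome (SAP 2.2.4), and protocol 5.2 lists "intravenous rehydration, and hospitalization" among the dichotomous outcomes.

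**Expected frequency.** "We estimate that only a small proportion (<5%) of enrolled subjects will be hospitalized" (protocol 4.2). The documents give no rate for other SAEs.

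**The concern.** There are two separate problems.

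First, the objective is a claim of no association, while the implied test can only detect a difference. With few events, non-significance is the likely result whether or not the drug does harm. Without an interval, the report would not say how large an excess remains possible.

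Second, the pooled SAE count mixes two kinds of event that the trial's own hypotheses expect to move differently. If the probiotic works, gastroenteritis admissions fall; if it causes other serious events, those rise. The any-SAE comparison sees only the sum. Even with no efficacy, the admissions add background variation and make a rise in other events harder to detect.

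The SAP already separates such events one section earlier. Section 7.4.1 leaves diarrhea, vomiting, fever and diaper rash out of the early side-effect test, partly because all but diaper rash belong to the efficacy outcomes. Section 7.4.2 makes no matching separation for SAEs.

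**Working it through.** **Inputs from the documents.** Two-sided test at 0.05 (protocol 5; SAP 3.3). Equal allocation (SAP 3.1). Target 970 (protocol V3.0, 1.4), so 485 per arm; after the 10% loss assumed in SAP 3.3, 485 × 0.90 ≈ 436 per arm. Design effect 25% to 15%, a relative risk of 0.15/0.25 = 0.60. Hospitalized: under 5%.

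**Assumptions, not in the documents.** Placebo gastroenteritis admissions of 1% to 5%; other SAEs rising from 2% to 4% (or 1% to 3%); the 0.60 relative risk carried over from the primary outcome to admissions; no child with both kinds of event, so the rates add; an unstratified z-test in place of the Mantel-Haenszel test.

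**The plan's own figure.** The documents give no sample size or power for SAEs, so the check is on the efficacy calculation:

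n per arm = [1.96 × √(2 × 0.20 × 0.80) + 1.2816 × √(0.25 × 0.75 + 0.15 × 0.85)]² / 0.10² = (1.109 + 0.719)² / 0.01 = 334.2, so 335 per arm and 670 in total. This matches.

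**Chance of a significant excess on probiotic.** With rates a (placebo) and b (probiotic), p = (a + b)/2, s0 = √(2p(1 − p)/n) and s1 = √((a(1 − a) + b(1 − b))/n):

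power = Φ[(b − a − 1.96 × s0)/s1].

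*Other SAEs alone, 2% vs 4%, n = 485.* s0 = 0.01095 and s1 = 0.01094, so (0.02 − 0.02146)/0.01094 = −0.13 and power = 45%.

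*All SAEs, 5% placebo admissions.* Placebo 5% + 2% = 7%; probiotic 3% + 4% = 7%. The difference is zero, so the harm-direction rejection rate is its null value, 2.5%. The fall in admissions removes 485 × 0.02 = 9.7 children, as many as the rise in other SAEs adds.

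*All SAEs, 1% placebo admissions.* Placebo 3.0%; probiotic 0.6% + 4% = 4.6%. s0 = 0.01228 and s1 = 0.01227, so (0.016 − 0.02407)/0.01227 = −0.66 and power = 26%. The offset is 485 × 0.004 = 1.9 children.

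Over the range (485 per arm, other SAEs 2% to 4%):

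| Admissions, placebo to probiotic | All SAEs | Pooled | Pooled, admissions unchanged | Other SAEs alone |
|---|---|---|---|---|
| 1% to 0.6% | 3.0% vs 4.6% | 26% | 36% | 45% |
| 2% to 1.2% | 4.0% vs 5.2% | 14% | 30% | 45% |
| 3% to 1.8% | 5.0% vs 5.8% | 8% | 26% | 45% |
| 5% to 3.0% | 7.0% vs 7.0% | 2.5% | 21% | 45% |

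The fourth column is dilution without any benefit on admissions; the step from there to the third column is the offset itself.

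With other SAEs at 1% to 3% and 5% admissions, the totals are 6% vs 6%: 2.5% pooled against 60% separately. At 436 per arm the separate figures are 41% (2% to 4%) and 56% (1% to 3%). Simulation of the 5% admissions cases with 200,000 runs agreed within about 2 points.

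**What an interval would show.** Half-width at 2% per arm: 1.96 × √(2 × 0.02 × 0.98/485) = 1.8 points. At 7% per arm: 1.96 × √(2 × 0.07 × 0.93/485) = 3.2 points. In the complete-offset case the all-SAE interval is about −3.2 to +3.2 points, which does not support a claim of no association.

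**The case against.** The other side has several good points.

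- **No SAE test is named.** The test is inferred from the words about a similar fashion, and protocol 5.1 speaks of tabulating adverse events, including serious ones, by arm. This stands as a limit on the wording. But if no test is meant, the SAE half of objective 2 has no specified comparison at all, so 7.4.2 needs text either way.
- **Other displays exist.** A reader might infer that the whole SAE assessment rests on the pooled test and that harm would go unseen. The documents do not support that. Tables by System Organ Class and Preferred Term, relatedness, expectedness, narratives and the medical monitor's review would show the events; hospitalization is compared separately; and invasive *L. rhamnosus* disease is its own primary safety endpoint. The offset affects the pooled comparison only.
- **Not every admission is clearly an SAE.** Protocol 8.3.3 does not count a presenting illness that has not worsened, and the SAP's general exclusion of listed symptoms leaves unclear whether an admission coded as diarrhea or vomiting counts. This stands, and is itself a reason to specify.
- **The rates are assumed.** This also stands. At 1% admissions the offset is partial, and even the separate comparison misses a rise from 2% to 4% more often than not (45%).
- **Excluding disease admissions has its own hazard.** Protocol 8.3.1 warns that some toxicities are hard to tell from gastroenteritis. If the probiotic worsened the illness, an exclusion would move that harm out of view. So the non-gastroenteritis set should stand beside the all-SAE comparison, not replace it.

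**Conclusion.** The point holds for the pooled comparison. The any-SAE difference test that 7.4.2 implies has no margin or interval and cannot support the SAE half of objective 2. Because it includes gastroenteritis admissions, its sensitivity to other serious events drops from 45% to between 26% and 2.5% over placebo admission rates of 1% to 5%. Those figures assume other SAEs rising from 2% to 4%, a 40% relative fall in admissions and 485 per arm. The offset therefore runs from partial to complete, and the documents do not fix where the trial would fall.

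A reader might also infer that the sponsor will declare safety from a non-significant p-value. No section sets such a rule; the gap is that nothing says how the objective will be concluded. This is a cheap improvement to the SAP, not a flaw in the safety surveillance.

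**What to change.** In SAP 7.4.2:

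1. Name the SAE comparison. State its time window, since the AE text mentions events before discharge while SAEs run to one year, and its grouping, since 7.4.2 uses assigned groups while 4.1.4 uses treatment received. State whether admissions coded to a listed symptom count.
2. Keep the all-SAE comparison. Add beside it, with equal standing, the proportion with any SAE other than an admission for the presenting gastroenteritis or dehydration within 14 days, classified before unblinding from MedDRA terms and narratives.
3. For both, report the stratified risk difference with its 95% confidence interval.
4. Word the conclusion on objective 2 as the largest excess that the upper limit does not exclude, not as no association.

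**Cost.** SAP text, one extra table and a small blinded classification step. SAEs are already MedDRA-coded with narratives, so no new data are needed. Some events will be misattributed between disease and drug, which is why all SAEs stay on display. The conclusion becomes a bound (about ±1.8 points around the observed difference at 2% per arm), which is less favourable than a statement of no association.

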## 7.5 Analysis of Tertiary Outcomes

Tertiary outcomes will be analyzed in a manner similar to the primary and secondary outcomes. Dichotomous outcomes will be compared between groups using the Mantel-Haenszel test, while continuous outcomes will be compared using the Van Elteren test. Both types of tests will be stratified by the randomization stratification factors: clinical center and duration of symptoms.

## 7.6 Analysis of Subgroups

There are 3 subgroup factors prespecified for formal analysis in this trial:

1. Age (under 1 year versus 1 and older)
2. Antibiotic useage during the 14 days prior to ED visit,
3. Infectious agent: virus, bacteria, parasite, or other/unidentified.

Rates of the primary study outcome will be reported by treatment arm for all prespecified subgroups. Secondary outcomes will also be reported by arm for all subgroups.

A “subgroup” effect will be declared to be significant only if the interaction between assigned treatment and the subgroup factor is significant in the appropriate statistical model testing for each particular interaction, at a significance level of  $0.05/3 = 0.017$ . These results must still be viewed with caution, given the number of outcomes. For the primary outcome, and other binary outcomes, logistic regression models will be used with a main effect for treatment, a main effect for the subgroup variable of interest, and an interaction between the subgroup variable of interest and the treatment. Interactions for continuous outcomes will be evaluated in a similar manner, using linear regression models. Interactions for count outcomes (missed days of daycare and work) will be evaluated using negative binomial regression models.

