## 2.3 Covariates

Although randomization should result in approximate balance between treatment groups with respect to critical baseline variables affecting the outcomes, additional exploratory analyses will be conducted to assess the effects of treatment after adjusting for baseline covariates in models for each outcome. The covariates considered are:

- baseline MVS (actual score),
- duration of symptoms prior to enrollment (<48 hours vs. 48 hours or more),
- age,
- gender,
- clinical center,
- breast-feeding status,
- antibiotic useage during the 14 days prior to ED visit,

- infective agent at baseline (e.g., norovirus, rotavirus),
- hydration assessment (Gorelick dehydration score),
- need for hospitalization from initial ED visit,

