### 3.2 Randomization and Blinding

#### 3.2.1 Method of Treatment Assignment

Randomization will be balanced among the study arms. Randomization will be stratified by clinical center and by duration of symptoms. Permuted blocks of lengths 2, 4, and 6 will be used for randomization. This trial will use a web-based system for randomization provided by randomize.net. Randomization/kit numbers will be provided in a scrambled order and separated into arms (A and B).

**Delivery of Randomization** Randomizations will be delivered to the clinical centers using a web-based system administered by randomize.net. This system will use each enrolled patient's clinical center and duration of symptoms (<48 hours vs. 48 hours or more) to deliver the next assigned treatment.

In this trial, there will be no "emergency backup" randomization, as we expect to be able to capture a sufficient number of patients.

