where  $n_1$  and  $n_2$  are, respectively, the number of subjects enrolled prior to and following the first interim analysis. Note that, if no enrichment is performed (i.e., accrual from the full population),  $Z$  is asymptotically equivalent to the usual z-statistic ignoring the stages. This final  $Z$  value will be compared to the quantiles of the standard normal distribution corresponding to the interim or final boundaries described in Section 6.2. A significant result will indicate efficacy in the population that was enrolled following the first interim analysis.

Simulations were performed to evaluate the performance of this design. Additional assumptions/considerations:

- The (untreated) outcome rate in the subpopulation with greater than 2 days of symptoms is 20%, while it is 30% in the other subpopulation.

- Each subpopulation accounts for 50% of the overall population.
- The normal approximation to the binomial distribution was used, rather than a chi-square or Mantel-Haenszel test.
- The interim analyses occur at 35% and 70% of target patient enrollment.

Several different treatment effect scenarios were simulated. The results show that the enrichment design will increase power when the treatment effect differs by subpopulation, but will have little impact on power if the treatment effect is the same in both subpopulations. One slight disadvantage is that, depending on outcome rates, the enrichment design will only accrue a subpopulation after the first interim analysis with probability 0.05–0.35 when, in fact, there is a homogeneous treatment effect.

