This outcome will be tabulated by treatment for each stratum (clinical center and duration of symptoms). A Mantel-Haenszel statistic, assessing the effect of treatment on the primary outcome controlling for strata, will be calculated to test the primary hypothesis. Summary statistics for the effect sizes will be given. For dichotomous outcomes, Mantel-Haenszel risk ratios will be reported to the DSMB at interim analyses. Choice of final summary statistic reported (e.g., risk difference, risk ratio, or odds ratio) will be based, in part, by which statistic is least variable across subgroups (i.e., shows the smallest degree of interaction across subgroups).

It is expected that, for both the final analyses as well as interim analyses, the asymptotic version of the Mantel-Haenszel test will be appropriate. This analysis will be performed using SAS PROC FREQ. In the case of low outcome counts, which may occur within strata at early interim analyses, the Mantel-Fleiss criterion will be assessed. If the criterion has a value less than 5, the exact version of the Mantel-Haenszel test will be used and the two-sided p-value will be defined as the sum of all probabilities of test statistics with point probabilities less than or equal to that of the observed value.

In the event any patients were randomized within an incorrect stratum (i.e., wrong duration of symptoms) due to misspecification at time of randomization, the actual rather than assigned category will be used in the above analysis.

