### 7.2.2 Additional Analyses of Primary Outcome

A secondary analysis of the primary outcome will test for treatment effect on the primary outcome using a logistic regression model with baseline MVS as a covariate. We will also analyze the MVS outcome as a continuous variable. For this analysis, treatment groups will be compared using a Van Elteren test, stratified by center and duration of symptoms.

We will perform further analyses of the MVS score outcomes by assessing the treatment effect after adjustment for covariates. The covariates that will be included have been described previously. A logistic regression model will be used for the indicator outcome of moderate-severe disease ( $MVS \geq 9$ ). Linear models will be used for the continuous MVS score. These models will be evaluated and adjustments will be made if any assumptions appear to be seriously violated. For example, a distribution other than the normal distribution may be used for the MVS score.

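### The subgroup interaction models in SAP 7.6 leave out the randomization strata; in the logistic models this slightly shrinks the interaction estimate and costs a little power

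*Combined protocol and SAP*

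**What the plan says.** All references are to SAP v1.2 unless stated.

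- **Allocation (3.2.1).** "Randomization will be stratified by clinical center and by duration of symptoms".
- **Primary test (7.2).** A Mantel-Haenszel statistic is used, "assessing the effect of treatment on the primary outcome controlling for strata". Children randomized under the wrong duration category are analyzed in their actual one.
- **Other main tests.** Both strata are named for the Van Elteren test of the continuous score (7.2.2), symptom durations and missed days (7.3.1), return visits (7.3.2), side effects and adverse events (7.4), and tertiary outcomes (7.5).
- **Subgroup models (7.6).** When the outcome is binary, the SAP states that "logistic regression models will be used with a main effect for treatment, a main effect for the subgroup variable of interest, and an interaction". For other scales, "Interactions for continuous outcomes will be evaluated in a similar manner, using linear regression models", and missed days use negative binomial regression. Neither center nor duration is mentioned. The threshold is 0.05/3, printed as 0.017.
- **Baseline-score model (7.2.2).** One secondary analysis of the primary outcome is done "using a logistic regression model with baseline MVS as a covariate". A further adjusted logistic model follows, for which "The covariates that will be included have been described previously". That list, in 2.3, holds baseline MVS, clinical center and symptom duration.
- **General rule (5.3).** The primary and unspecified other analyses are to be stratified by center. Duration is not mentioned.
- **Duration as prognostic (4.3).** The enrichment simulations assume that the "outcome rate in the subpopulation with greater than 2 days of symptoms is 20%, while it is 30% in the other subpopulation".

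**The concern.** A trial that stratifies its allocation would normally carry the strata into its models. The SAP does so for its main tests and drops them, as written, in 7.6. It treats duration as prognostic in its own simulations, and 5.3 justifies stratifying by center because centers may differ at baseline.

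Two things are at stake. In a logistic model, leaving out prognostic factors moves the fitted log-odds ratio toward zero, which weakens a test already held to about 0.017. The text also leaves a choice open: 5.7 has two statisticians program the analyses independently, and one could add center on the strength of 5.3 while the other fits the three listed terms.

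**Working it through.** **1. The plan's own figure.** For 25% v 15%, two-sided alpha 0.05 and 90% power, with pooled variance under the null and no continuity correction:

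n per arm = [1.960·√(2·0.20·0.80) + 1.282·√(0.25·0.75 + 0.15·0.85)]² / 0.10² = (1.109 + 0.719)² / 0.01 ≈ 334.2, so 335 per arm and 670 in total.

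This matches SAP 3.3, and all eight rows of its power table reproduce at 335 per arm. The inflation also reproduces: 670/0.90 = 744; 744/0.92² = 879; 879 × 1.02 = 897.

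**2. Inputs for the interaction check.**

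- From the documents: N = 970 (protocol v3.0, section 1.4); 1:1 allocation; control rates 30% and 20% in two duration halves (SAP 4.3); interaction alpha 0.05/3 = 0.0167, critical value 2.394.
- Effect contrast: the planned effect has odds ratio (0.15/0.85)/(0.25/0.75) = 0.529. I assume it holds in one subgroup level and is absent (1.0) in the other, so the true interaction is −ln 0.529 = 0.636.
- Also assumed: a 50/50 subgroup unrelated to the strata; 10 equal centers with logit effects at evenly spaced normal quantiles, nominal SD 0, 0.3 or 0.5. The documents give no figure for variation between centers.

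**3. Method.** Logistic models were fitted to expected cell counts, once with the three terms of 7.6 and once adding duration and center. Then z = estimate/SE, and power = Φ(z − 2.394) + Φ(−z − 2.394).

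| Center SD | Model | Log-OR | SE | z | Power |
|---|---|---|---|---|---|
| 0 | without strata | 0.629 | 0.313 | 2.007 | 34.9% |
| 0 | with strata | 0.636 | 0.315 | 2.018 | 35.3% |
| 0.3 | without strata | 0.621 | 0.311 | 1.994 | 34.5% |
| 0.3 | with strata | 0.636 | 0.315 | 2.016 | 35.3% |
| 0.5 | without strata | 0.607 | 0.308 | 1.970 | 33.6% |
| 0.5 | with strata | 0.636 | 0.316 | 2.013 | 35.2% |

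The losses are 0.4, 0.8 and 1.6 points. Ten quantiles have an SD a little below the nominal value; scaling them to exactly 0.5 gives a log-OR of 0.604 and a loss of about 1.7 points.

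**4. Where the loss comes from.** In every pair the SE is smaller without the strata. The estimate shrinks proportionally more: at SD 0.5, 0.607/0.636 = 0.955 against 0.308/0.316 = 0.975. So z falls.

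**5. Sensitivity.** At the SAP's target of 900, power goes from 32.3% to 32.6% (SD 0) and from 31.0% to 32.4% (SD 0.5) when the strata are added. With one subgroup level holding 10% of children (N = 970, SD 0.3), it goes from 12.6% to 12.9%. With the same effect in both levels, the interaction estimate is zero in both models, so under these assumptions the omission creates no false signals.

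**6. Overall treatment effect.** As a stand-in for the baseline-score model (its link to outcome is not given, so baseline MVS was left out), a common odds ratio of 0.529 at alpha 0.05 gives power without and with strata of 96.9% and 97.0% (SD 0), 96.4% and 97.0% (SD 0.5), and 95.5% and 97.0% (SD 0.8).

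**The case against.** **Section 5.3 may already supply center.** That reading is possible, but the section does not say which other analyses it covers, and it is silent on duration. The specific list in 7.6 has no stratum in it. Section 5.5 also considers duration as a subgroup factor, but that puts it in its own model only, not in the models for age, antibiotic use and infectious agent.

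**Section 7.2.2 already has an adjusted model.** This stands. The further logistic model includes baseline MVS, center and duration. A reader might infer from the baseline-score model that the SAP never adjusts a regression of the primary outcome for the strata; section 2.3 shows otherwise.

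**A three-term interaction model is valid.** This also stands. The models with and without strata estimate slightly different odds ratios (conditional and marginal), so the shrinkage is a property of the scale, not an error. The SAP itself asks for caution with subgroup results.

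**The strata may cause trouble.** Center terms can produce empty or near-empty cells, most plausibly in the four-level infectious-agent model. That is a real but manageable cost.

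**A tempting stronger reading is that the models lose precision.** For the logistic models the SE moves the other way. Loss of precision is a fair description for the linear models of continuous outcomes, but the documents give no SD from which to size it.

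**Conclusion.** The point holds as a small inconsistency in 7.6: its interaction models omit strata that the main tests control for. In the logistic models the cost is a slightly attenuated interaction and about 0.4 power points on the documents' own rates by duration. It rises to about 0.8 to 1.7 points if center SD is 0.3 to 0.5 on the logit scale. These sizes rest on the assumed center variation, 10 equal centers, an even subgroup split unrelated to the strata, and an effect confined to one subgroup level. The linear and negative binomial models were not sized.

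A reader might infer that the missing strata explain weak subgroup tests. They do not: power is near 35% with or without them, even for this strong contrast. Nor is the primary conclusion touched, since the primary test controls for both strata.

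**What to change.** In 7.6, state that every interaction model includes clinical center and symptom duration (under 48 hours v 48 hours or more) as main effects, using the actual duration category as 7.2 does. In the model where duration is itself the subgroup, only center is new. Add a fallback for sparse cells, such as pooling small centers or conditioning on stratum, and name the infectious-agent model as the likely case.

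For consistency, the same terms may be added to the baseline-score model in 7.2.2; little depends on it.

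The cost is a sentence or two in the SAP and some degrees of freedom for center. No new data are needed, because the randomization system requires both variables. The small downside is the sparse-cell handling, which should be fixed before arm-level subgroup results are seen.
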